If nonintubation anaesthesia for laryngomicrosurgery can be performed with nerve block and intravenous anesthetic medicine, the cardiovascular risks may decrease because of avoiding CO2 retention by maintaining patient's spontaneous breathing function. The feasibility and safety of nonintubated LMS with spontaneous breathing was evaluated in this case series.

Method

We divide the patients who need laryngoscopy microsurgery into three groups. The first group is general anesthesia with endotracheal tube intubation, the second group is non-intubation with muscle relaxant administered; the third group is non-intubation without muscle relaxant.

The three groups will perform arterial blood oxygen analysis (collecting PaO₂, PaCO₂, pH, HCO₃-data) before intubation, before muscle relaxant administration and before SLNB, after the operation and 15 minutes after transferring to the recovery room, as well as the pressure of the surgeons and the degree of completion of the operation to analyze the difference between intubated general anesthesia and non-intubation anesthesia.

Results

Last year, we passed the in-hospital plan (2021/04/07) and have been included (Table 1). There are 15 males and 14 females, all of whom have completed the trial phase without complications. Group 1 earns 11 people, Group 2 earns 7 people, and Group 3 earns 11 people.

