Ho3: There is less sore throat in the nonintubation group than in the intubation group.

Ho4: Non-intubation and no muscle relaxation may lead to less postoperative pulmonary complications.

Ho5: In the non-intubation group, no muscle relaxants are more suitable for long-term surgery than those with muscle relaxants.

Statistical analysis (the statistical analysis tool will use IBM SPSS version 20):

- 1 、 The sample characteristic data will be expressed as average, SD, and median, and the category variables will be displayed in the form of count and percentage.
- 2 、 The 95% confidence interval will show the original data and the change from the baseline.
- 3 、 The difference between the three groups was analyzed using one-way ANOVA to analyze the comparison between the intubation and non-intubation groups for drug administration, the presence or absence of complications, the severity and

the degree of completion of the operation.

- 4 ‧ The differences between the groups will be evaluated by chi-square test or Fisher's exact test.
- 5 ‧ Unless otherwise stated, all statistical tests will be two-way and evaluated at a significance level of 0.05.

Sample size calculation :

The main purpose of the study will focus on the completion of surgery and the occurrence of complications. In order to obtain the total number of participants in the study, a sample size will be calculated to detect a difference in incidence reduction of 25%. A statistical power of 80%, a 5% alpha and up to 10% possible sample loss. Therefore, each group will require 30 patients (90 in total). Considering the number of patients undergoing laryngoscope microsurgery each year, we estimate that there may be a total of 45 patients within a year. After meeting the inclusion criteria and obtaining patient consent, 45 patients will be included in the treatment plan in the first year, and the remaining sample size will be completed next year.

Primary outcome(2nd year) :

- 1 ‧ Less carbon dioxide retention and less hypercapnia.
- 2 ‧ Reduce postoperative lung complications.

Statistics from 10/20/2020 to 5/11/2021 :

Table I-i. Baseline demographics

Variable	G1(n=11)		G2(n=7)		G3(n=11)		p-value
	Mean	SD	Mean	SD	Mean	SD	
Age	52.0	13.9	46.9	8.4	51.7	14.2	0.66
BMI	26.4	5.5	24.5	3.5	25.1	2.5	0.78

Table I-ii. Baseline demographics

Variable	G1(n=11)		G2(n=7)		G3(n=11)		p-value
	n	(%)	n	(%)	n	(%)	
Sex							
male	7.0	63.6	3.0	42.9	5.0	45.5	0.60
female	4.0	36.4	4.0	57.1	6.0	54.5	
ASA							

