ASA I	3.0	27.3	3.0	42.9	9.0	81.8	0.04
ASA II	8.0	72.7	4.0	57.1	1.0	9.1	
ASA III	0.0	0.0	0.0	0.0	1.0	9.1	
Medical history							
HTN	3.0	27.3	0.0	0.0	4.0	36.4	0.20
CVA	1.0	9.1	0.0	0.0	0.0	0.0	0.43
CVD	1.0	9.1	0.0	0.0	3.0	27.3	0.22
DM	1.0	9.1	0.0	0.0	2.0	18.2	0.46
Endocrine	1.0	9.1	2.0	28.6	1.0	9.1	0.43
Genitourinary	0.0	0.0	1.0	14.3	0.0	0.0	0.20
HPL	1.0	9.1	1.0	14.3	0.0	0.0	0.47
Neurologic	0.0	0.0	1.0	14.3	1.0	9.1	0.47
Hepatitis B	1.0	9.1	1.0	14.3	0.0	0.0	0.47

Table I-ii. During the acceptance period, group 3 included 1 ASA3 case, and the remaining groups have not yet encountered ASA3 cases.

Table II. Arterial blood oxygen changes during surgery

Variable	G1(n=11)		G2(n=7)		G3(n=11)		p-value
	Mean	SD	Mean	SD	Mean	SD	
Before surgery							
pH_1	7.4	0.0	7.3	0.0	7.4	0.0	0.34
PaCO2_1	49.5	2.5	53.6	9.5	51.3	6.5	0.58
PaO2_1	321.2	79.6	451.9	108.6	377.5	196.6	0.14
SO2_1	99.7	0.8	99.9	0.0	99.8	0.4	0.50
HCO3-_1	28.3	1.7	28.6	3.3	28.8	1.6	0.67
In surgery							
pH_2	7.3	0.0	7.2	0.1	7.3	0.0	0.00
PaCO2_2	54.4	7.6	86.4	21.7	55.5	10.8	0.00
PaO2_2	186.9	64.0	321.8	128.2	341.9	136.9	0.02
SO2_2	99.3	1.1	99.6	0.5	99.7	0.5	0.48
HCO3-_2	27.7	1.9	31.8	4.1	29.1	2.7	0.06
After surgery							
pH_3	7.4	0.0	7.4	0.1	7.4	0.0	0.07
PaCO2_3	43.6	4.0	45.1	9.0	43.3	5.7	0.78
PaO2_3	123.3	63.1	110.8	16.1	116.3	29.6	0.77
SO2_3	98.0	1.5	98.2	1.0	98.3	1.4	0.81
HCO3-_3	25.8	1.7	26.3	2.9	27.0	2.5	0.55

Table II. During the operation, the PaCO2 value of the second group was >80mmHg.

Table III. Discomfort after surgery

Variable	G1(n=11)		G2(n=7)		G3(n=11)		p-value
	n	(%)	n	(%)	n	(%)	
Sore throat	3.0	27.3	0.0	0.0	4.0	36.4	0.20
Hoarseness	6.0	54.5	6.0	85.7	7.0	63.6	0.39
Difficulty breathing	0.0	0.0	0.0	0.0	1.0	9.1	0.43

Table III. One case in group 3 reported dyspnea in the recovery room. In most cases of laryngoscope surgery, the voice is required to be silenced after the operation, so the case cannot make a sound.

Table IV. Side effects after surgery

Variable	G1(n=11)		G2(n=7)		G3(n=11)		p-value
	n	(%)	n	(%)	n	(%)	
nausea	0.0	0.0	0.0	0.0	1.0	9.1	0.43
Vomiting	1.0	9.1	0.0	0.0	1.0	9.1	0.71
Nausea and vomiting	0.0	0.0	0.0	0.0	1.0	9.1	0.43

Table IV. One patient in group 1 had the side effect of vomiting.

In group 3, 1 case had nausea and vomiting.

Table V. Three stages of vital signs

Variable	G1(n=11)		G2(n=7)		G3(n=11)		p-value
	Mean	SD	Mean	SD	Mean	SD	
Before surgery							
BT	36.0	0.5	36.3	0.4	36.2	0.5	0.61
SpO2	98.8	1.3	98.1	1.5	97.7	2.1	0.46
NBPs	136.5	11.2	121.7	7.5	124.0	18.5	0.04

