Table VII. The surgeon was satisfied with the surgical satisfaction of the three groups, but the stress intensity was higher when performing non-intubation and nerve block surgery.

Table VIII. Dunnett T3 Post-hoc tests of during the operation

variable			M.D (I-J)	SE	p-value
pH_2	G1	G2	.135961*	.024404	.001
		G3	-.013455	.017469	.825
	G2	G1	-.135961*	.024404	.001
		G3	-.149416*	.024411	.000
	G3	G1	.013455	.017469	.825
		G2	.149416*	.024411	.000
PaCO2_2	G1	G2	-32.0468*	8.5162	.020
		G3	-1.1636	3.9766	.987
	G2	G1	32.0468*	8.5162	.020
		G3	30.8831*	8.8281	.023
	G3	G1	1.1636	3.9766	.987
		G2	-30.8831*	8.8281	.023
PaO2_2	G1	G2	-134.9130	52.1401	.087
		G3	-155.0273*	45.5545	.012
	G2	G1	134.9130	52.1401	.087
		G3	-20.1143	63.6399	.984
	G3	G1	155.0273*	45.5545	.012
		G2	20.1143	63.6399	.984

*. The M.D is significant at the 0.05 level.

[figure not shown]
Table VIII. Found the following situation :

1. In the non-intubated and muscle relaxant group (G2), the pH value during the operation was lower than the non-intubated and nerve-blocking group (G3), and lower than the normal value (7.35-7.45) .
2. During the operation, the PaCO2 of the non-intubated and muscle relaxant group (G2) was significantly higher than intubated group and also higher than the non-intubated and nerve-blocking group.
3. The PaO2 value of the intubation group (G1) during the operation was lower than that of the non-intubation group.

KSVGH20-C9-09 CASE REPORT

No:	Consent Signed _(MM/DD/YYYY) :	Operation Date:				
Patient status : _____						
Reason for quitting :						
Gender:	Age:	Weight _(kg) :	Height _(cm) :	BMI:	ASA:	
BASELINE MEDICAL/SURGICAL HISTORY :						
Time to enter the room :		Before induction BT:_____ SpO ₂ :_____ BP:___/___ PR:___ RR:___				
Study Group		Operation time				
Induction time		Anesthesia time				
Endo size & pressure		Propofol dose		Rocuronium dose		
		Fentanyl dose		Cisatracurium dose		
GAS		Before(:) G1: intubation ; G2: cis and scc ; G3: SLNB		OP end(:)		
pH				POR(:)		
PaCO ₂						
PaO ₂						
SO ₂ %						
HCO ₃ ⁻						
Time to post anesthesia recovery room :						
BT:_____ SpO ₂ :_____ BP:___/___ PR: ___ RR:_____						
PACU	Time	oxygen	respiration	circulation	consciousness	activity

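### Most printed p-values for continuous variables cannot come from one-way ANOVA, the only continuous-data test the plan names; the plan should name its tests and the tables be recomputed

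*Protocol*

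**What the plan says.** In the Protocol, section C (Methods and study procedure), Statistical analysis, item 3 reads "The difference between the three groups was analyzed using one-way ANOVA". Item 4 adds "The differences between the groups will be evaluated by chi-square test or Fisher's exact test", which serves categorical data. Item 5 sets the threshold: "all statistical tests will be two-way and evaluated at a significance level of 0.05". No Welch test, rank test or post-hoc procedure is named.

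The same section prints results for the first 29 patients: "Group 1 earns 11 people, Group 2 earns 7 people, and Group 3 earns 11 people". Tables I-i, II, V, VI (operation time) and VII (stress index) give a mean and SD per group and one p-value for each continuous variable, without saying which test produced it. The two largest are "Table II. Arterial blood oxygen changes during surgery" and "Table V. Three stages of vital signs". Pairwise comparisons then appear under "Table VIII. Dunnett T3 Post-hoc tests of during the operation".

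**The concern.** A p-value from one-way ANOVA is fixed by the group means, SDs and sizes. Anyone with the printed tables can therefore check whether the stated test was the one applied. For most continuous rows it was not, or the printed value is wrong.

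The final tables for 90 patients could not then be reproduced from the plan. The choice of test would also stay open after group results have been seen.

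A second issue is fit. The intraoperative PaCO2 SDs differ widely, and the largest belongs to the smallest group. That is the configuration in which ordinary ANOVA rejects too often. Carbon dioxide retention is listed as a second-year primary outcome, so the choice of test matters there. The use of Dunnett T3 in Table VIII, a procedure for unequal variances, suggests that the authors recognised this without carrying it into item 3.

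**Working it through.** **Inputs.** Means, SDs and p-values come from Tables I-i, II, V, VI and VII, with n = 11, 7 and 11 from the column heads. There are 36 continuous rows: 2 in Table I-i, 15 in Table II, 17 in Table V, and one each in Tables VI and VII.

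**Do the printed inputs hold together?** Table VIII gives unpooled standard errors that can be rebuilt from Table II:
- PaCO2, G1 vs G2: √(7.6²/11 + 21.7²/7) = 8.516; printed 8.5162.
- PaO2, G1 vs G2: √(64.0²/11 + 128.2²/7) = 52.16; printed 52.1401.

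Both agree with full group sizes. Pearson chi-square also reproduces all eight categorical rows checked (for example sex 0.60, ASA 0.04, sore throat 0.20, hoarseness 0.39). The mismatch below therefore lies in the continuous tests.

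**Formula.** F = [Σnᵢ(mᵢ − m)²/2] / [Σ(nᵢ − 1)sᵢ²/26], on 2 and 26 degrees of freedom.

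**Worked row.** The document prints "HCO3-_2 27.7 1.9 31.8 4.1 29.1 2.7 0.06".
- Weighted mean: (11×27.7 + 7×31.8 + 11×29.1)/29 = 29.22.
- Between-group sum of squares: 72.17.
- Within-group sum of squares: 10×1.9² + 6×4.1² + 10×2.7² = 36.1 + 100.86 + 72.9 = 209.86.
- F = (72.17/2)/(209.86/26) = 36.08/8.07 = 4.47, so p = 0.021. The printed value is 0.06.

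**All rows.** Every mean and SD was moved over its rounding interval (±0.05), and the printed p was allowed ±0.005. No admissible values give the printed p in 21 of 36 rows (58%): 2 in Table I-i, 7 in Table II and 12 in Table V. The other 15 are compatible, several only because rounding leaves them uninformative (pH, SO2 and body temperature). Selected rows:

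| Row | Printed p | ANOVA p (rounding range) | Welch p |
|---|---|---|---|
| HCO3-, end of operation | 0.06 | 0.021 (0.016–0.028) | 0.067 |
| NBPs, before surgery | 0.04 | 0.056 (0.053–0.059) | 0.013 |
| NBPd, before surgery | 0.06 | 0.041 (0.038–0.044) | 0.086 |
| PR, before surgery | 0.46 | 0.87 (0.854–0.877) | 0.81 |
| NBPs, after surgery | 0.20 | 0.050 (0.048–0.052) | 0.126 |
| RR, after surgery | 0.63 | 0.90 (0.860–0.928) | 0.91 |
| PaO2, end of operation | 0.02 | 0.0075 | 0.007 |
| PaCO2, end of operation | 0.00 | 0.00005 | 0.010 |
| Operation time | 0.00 | 0.003 | 0.010 |

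Only the first three lie on the other side of 0.05 from the printed value over their whole rounding range. Postoperative NBPs straddles 0.05 and is not counted.

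**Other candidate tests.** Welch's ANOVA is compatible with 12 of 36 rows and Brown-Forsythe with 15, so neither explains the column. A rank test cannot be checked from means and SDs, except for the stress index, whose integer scores can be enumerated. There the printed 0.01 matches ANOVA (about 0.01) and not Kruskal-Wallis (0.002–0.005).

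**Type I error for PaCO2.** With normal data, equal means and SDs of 7.6, 21.7 and 10.8, simulation gives ordinary ANOVA about 12% at 11/7/11 and about 6.5% at 30 per group. Welch's test holds about 5% at both.

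**The case against.** Four points on the other side carry weight.

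- **The scope of item 3 is inferred.** Its own list covers drug administration, complications, severity and surgical completion. Blood gases and vital signs are not on it, and a separate statistical analysis plan may say more. This softens the contradiction. Still, item 3 speaks of the three-group difference in general, and ANOVA is the only named test that fits these rows.
- **The three crossings exist only against ordinary ANOVA.** Under Welch's test all three return to the printed side of 0.05 (0.067, 0.013, 0.086). They are two baseline pressures and one bicarbonate value, none of which appears in Ho1 to Ho5 or in either primary-outcome statement. This stands in full.
- **The count assumes complete data.** With up to one unreported missing value per group, 20 rows remain impossible and two crossings survive (HCO3- and preoperative NBPs). With up to two, 16 rows remain impossible and no crossing is certain. No missing values are reported, but Table VIII confirms full n only for PaCO2 and PaO2.
- **The tables are interim data on 29 patients.** They do not prove how the final analysis will be run.

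A reader might infer that the trial's PaCO2 contrasts carry wrong error bars from a pooled variance. The document does not support that: its only PaCO2 contrasts, in Table VIII, already use unpooled standard errors.

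**Conclusion.** The inconsistency is real and should be corrected. About 21 of 36 continuous p-values cannot come from the named test. A few of these are narrow misses: for age the lowest possible ANOVA value is 0.670 against a printed 0.66. Others are far outside rounding. The post-hoc test in use is not in the plan.

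The consequence is limited to reproducibility and to a test choice left open after group results were seen. It does not reach the conclusions: intraoperative PaCO2, PaO2 and operation time are significant as printed, under ANOVA and under Welch. The excess type I error for PaCO2 is material at the present unequal sizes but modest at the planned 30 per group, and it assumes that the interim SDs persist.

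Two stronger readings are not supported. One is that a rank test was secretly substituted: the stress index argues against a single rank test throughout, so the column may mix tests or contain errors. The other is that the carbon dioxide finding depends on the choice of test, which it does not.

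**What to change.** In item 3, name the tests by type of variable:
- **Continuous measurements** (blood gases, vital signs, operation time and similar): Welch's ANOVA with Dunnett T3 pairwise comparisons, which agrees with Table VIII.
- **Stress index (1–5):** an exact Kruskal-Wallis test. Group 1 has mean 1.0 and SD 0.0 on a scale whose minimum is 1, so its variance is zero and Welch's weight n/s² is undefined.

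Recompute the continuous p-values in Tables I, II, V, VI and VII with these tests before the remaining 61 patients are analysed. State which test produced each value now printed, and give n per row wherever data are missing.

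The cost is a sentence or two in the plan and a re-run of existing tables. Some p-values become less favourable: PaCO2 at the end of the operation moves from a printed 0.00 to about 0.01. Because 29 patients' results are already known, the choice should be justified by the unequal variances and the ordinal scale, and not by the p-values it yields.

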During the operation, a pulse oximeter will be used to monitor and record the patient's oxygen saturation. The patient's gender, height, weight, BMI, age, past medical history, ASA classification, type of laryngoscopic surgery, operation time, lesion location, blood loss, and anesthesia records will be kept.

All three groups of patients will use radial artery catheters. In addition, the three groups performed arterial blood gas analysis (including: PaO₂, PaCO₂, pH, HCO₃⁻) at the following times to understand the difference of pCO₂ in different groups and as a secondary result.

The first period to measure those variables is before each set of surgery are follows:

The first group is before tracheal intubation.

The second group was before the administration of muscle relaxants.

The third group is before applying superior laryngeal nerve block bilaterally.

The second period to measure those variables is the end of the operation.

The third period to measure those variables is 15 minutes after entering the recovery room.

All the anesthesia time, operation start time and operation end time of the three groups will be recorded, and the relationship between them will be discussed.

After the operation, the surgeon and the patient will be asked to do a questionnaire survey in order to understand whether the non-intubation anesthesia laryngoscope microsurgery of the self-breathing causes obstruction or other difficulties for the operator, as well as the patient's postoperative recovery, surgical satisfaction and operation After scoring. Finally, the surgeon's score on the degree of surgical completion was taken as the primary outcome.

Conditions for participating in this research project:

- Subjects are between 20-80 years old.
- Patients undergoing laryngoscope microsurgery.

- Anesthesiologists rated ASA as between I and III.

If those who are included have any of the following conditions, you will not be able to participate in this research project:

- Having drug dependence and drinking habits.
- Abnormal heart, liver and kidney function.
- Allergic reactions to narcotic drugs.
- Emergency surgery.
- pregnancy.
- Refuse to participate.

This study will explore the following assumptions:

Ho1: The intraoperative field of vision of the nonintubation group is clearer than that of the intubation group.

Ho2: Non-intubation and no muscle relaxation has less carbon dioxide retention and less hypercapnia.

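### The listed tests compare three groups at once, while Ho1, Ho3 and Ho5 are two-group contrasts and Ho2 and Ho4, which return as second-year primary outcomes, name no comparator

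*Protocol*

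**What the plan says.** The hypotheses are listed in Protocol section C, just before the statistical analysis. Ho1 (a clearer surgical view) and Ho3 (fewer sore throats) set non-intubated patients against intubated ones. Ho5 sets G3 against G2 on suitability for long operations. These three name both sides.

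The other two name only one. On blood gases the Protocol has "Ho2: Non-intubation and no muscle relaxation has less carbon dioxide retention and less hypercapnia". On the lungs, its wording is "Ho4: Non-intubation and no muscle relaxation may lead to less postoperative pulmonary complications". The list of second-year primary outcomes repeats the content of both, again with no comparator.

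The tests follow in the statistical analysis. Item 3: "The difference between the three groups was analyzed using one-way ANOVA to analyze the comparison between the intubation and non-intubation groups". It is to be applied to drugs given, complications, their severity and surgical completion. For categorical data, item 4 has "The differences between the groups will be evaluated by chi-square test"; Fisher's test is the alternative, and no pair or pooling is named. Item 5 sets the level: "all statistical tests will be two-way and evaluated at a significance level of 0.05".

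The first-year tables show how this was applied. Tables I to VII give one p-value per variable across the three groups. Table VIII adds Dunnett T3 pairwise tests for intraoperative pH, PaCO2 and PaO2. Items 1 to 5 mention no pairwise procedure.

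**The concern.** An overall three-group test asks whether the groups differ anywhere. None of the five hypotheses asks that. A significant overall result does not say which groups differ. A non-significant one does not answer a question about one particular pair.

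The open comparator in Ho2 and Ho4 matters more, because these are primary outcomes for the second year. The phrase about no muscle relaxation does not identify the other side: section C gives a relaxant to G1 as well as to G2. G3 could therefore be compared with G1, with G2 or with both. If these comparisons give different answers, the primary question has no single answer until the comparator is fixed, and it would be fixed after the first-year results are known.

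**Working it through.** **Inputs.** Table II, intraoperative PaCO2, mean (SD): G1 54.4 (7.6), n = 11; G2 86.4 (21.7), n = 7; G3 55.5 (10.8), n = 11. Table III, sore throat: 3/11, 0/7, 4/11. Table VII, stress index: 1.0 (0.0), 1.9 (1.2), 2.0 (0.8).

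**1. Overall PaCO2 test.** The grand mean is 62.54. The between-group sum of squares is 5259.1 on 2 df. The within-group sum is 10×7.6² + 6×21.7² + 10×10.8² = 4569.3 on 26 df. F = (5259.1/2)/(4569.3/26) = 15.0, p = 0.00005, which agrees with the printed 0.00.

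**2. Pairwise PaCO2.** SE = √(s₁²/n₁ + s₂²/n₂), with Welch df. The p-value comes from the studentized maximum modulus for three comparisons (Dunnett T3).

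| Pair | Difference | SE | T3 p, recomputed | T3 p, Table VIII | Unadjusted Welch 95% CI |
|---|---|---|---|---|---|
| G1 − G2 | −32.0 | √(5.25+67.27) = 8.52 | 0.020 | .020 | −52.2 to −11.8 |
| G3 − G2 | −30.9 | √(10.60+67.27) = 8.82 | 0.023 | .023 | −51.3 to −10.5 |
| G3 − G1 | +1.1 | √(10.60+5.25) = 3.98 | 0.989 | .987 | −7.3 to +9.5 |

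Table VIII is reproduced within rounding. G2 differs from both other groups, and G1 and G3 do not differ detectably. Ho2 is supported against G2, and there is no sign of it against G1.

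**3. What pooling would do.** Taking G2 and G3 together as non-intubated gives a mean of (7×86.4 + 11×55.5)/18 = 67.5, against 54.4 in G1 (Welch p = 0.029). Non-intubation then looks worse for CO2, only because of G2.

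**4. A categorical outcome.** For sore throat the expected counts are 7/29 of each group: 2.66, 1.69, 2.66. The three-group chi-square is 3.18 on 2 df, p = 0.203; Table III prints 0.20. The printed value is therefore the three-group test. Ho3 asks something else. Pooled, it is 4/18 against 3/11 (Fisher p = 1.0). By arm, it is G2 vs G1 p = 0.25 and G3 vs G1 p = 1.0. None of these is in the table.

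**5. Stress index.** From the printed values, F(2,26) = 5.49, p = 0.010; Table VII prints 0.01. The note under the table attaches the higher stress to non-intubated surgery under nerve block, the label that the notes to Table VIII use for G3. Yet G3 − G2 is 2.0 − 1.9 = 0.1, SE = √(0.8²/11 + 1.2²/7) = 0.51, Welch p = 0.85. The overall p does not separate G3 from G2.

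**The case against.** Four objections deserve weight.

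**The authors read the CO2 result correctly.** A reader might infer that a result driven by G2 would be taken as support for the relaxant-free technique in general, including against intubation. The Protocol does not support that. Its results summary states the G3 advantage against the relaxant group, the notes to Table VIII say that G2 is higher than both others, and the table prints .987 for G1 vs G3. This objection stands for PaCO2. It does not supply a comparator for the primary outcome, and it does not cover variables without pairwise tests.

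**The comparator in Ho2 can be inferred.** Section B attributes CO2 retention to apnoea under relaxants, and section D presents the nerve block as their replacement. Both point to G2. This largely stands for Ho2. It does not for Ho4, because section B also links relaxants in intubated anaesthesia to pulmonary complications, so G1 is equally plausible there.

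**Item 3 does not list blood gases.** True. PaCO2 shows that the comparator decides the answer, through Tables II and VIII; it is not an outcome that the wording of item 3 governs.

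**Post-hoc procedures may sit in an SAP.** Also true, so the absence of a pairwise method would not be a finding by itself. Describing a three-group test as the intubation comparison, and leaving a primary hypothesis without its second group, are faults in the Protocol text.

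The note to Table VII can also be defended as a G3 vs G1 statement, which the printed means and SDs support (T3 p about 0.006). What they do not support is setting G3 apart from G2.

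**Conclusion.** The point holds as a mismatch between hypotheses and tests. It does not show that the first-year CO2 results were misread. Item 3 is wrong as written. Ho1, Ho3 and Ho5 have no named contrast among the listed tests, and the first-year categorical results carry three-group p-values only. Ho2 and Ho4 lack a comparator while serving as second-year primary outcomes.

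The size is clearest for intraoperative PaCO2: the same data give −30.9 mmHg (T3 p = .023) or +1.1 mmHg (T3 p = .987) according to the comparator. The figures rest on rounded summary statistics from 29 patients, with only 7 in G2. The interval for G3 − G1, −7.3 to +9.5 mmHg, shows no evidence of a difference; it does not establish equality. It would also go too far to say that all five hypotheses are precise contrasts, since only three name both sides and Ho1 and Ho3 leave the pooling of G2 and G3 open.

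**What to change.** 1. **Ho2:** state G3 vs G2 as the comparison, as the rationale implies, and report G3 vs G1 separately. Use the same wording in the second-year primary outcome.
2. **Ho4:** the sponsor should state whether the comparator is G2, G1 or each separately, here and in the primary outcome.
3. **Item 3:** stop describing the three-group ANOVA as the intubation vs non-intubation comparison.
4. **Items 3 and 4:** make the named contrast the test of each hypothesis, with the difference and its 95% CI. For Ho1 and Ho3, choose either pooled G2+G3 vs G1 or each arm vs G1. Ho5 is G3 vs G2.
5. **Methods:** write into the plan the Dunnett T3 procedure already used, for continuous outcomes. For categorical outcomes use Fisher's exact test, with a multiplicity adjustment where a hypothesis has more than one pair.

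The cost is the wording of two hypotheses, the matching primary outcomes and two analysis items, plus slightly more analysis work and somewhat larger adjusted p-values. No new data are needed.

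### The one-way ANOVA named for the three-group comparison assumes equal variances, which the trial's own PaCO2 data contradict; the excess error is modest at 30 per group and larger if group 2 stays short

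*Protocol*

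**What the plan says.** In section C of the protocol, under statistical analysis, item 3 reads "The difference between the three groups was analyzed using one-way ANOVA". It goes on to list what is compared: "comparison between the intubation and non-intubation groups for drug administration, the presence or absence of complications, the severity and", and then the degree of completion. Blood gases are not in that list. Item 4 adds only the chi-square and Fisher's exact tests. Item 5 sets the level: "Unless otherwise stated, all statistical tests will be two-way and evaluated at a significance level of 0.05". No item mentions equal or unequal variances, or a follow-up procedure for pairs of groups.

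PaCO2 has two roles. The methods text treats it as a secondary result, while the second-year primary outcomes begin with carbon dioxide retention and hypercapnia.

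The interim data are in the same document. Group sizes are given as "Group 1 earns 11 people, Group 2 earns 7 people, and Group 3 earns 11 people". Table II has this row (mean and SD for each group in turn, then the p-value): "PaCO2_2 54.4 7.6 86.4 21.7 55.5 10.8 0.00". Table VIII then reports "Dunnett T3 Post-hoc tests of during the operation". The sample size paragraph plans 30 patients in each group, 90 in total.

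**The concern.** The classical one-way ANOVA uses one pooled variance for all groups. When true variances differ, its real type I error departs from the nominal level. The direction depends on the group sizes: if the noisiest group is also the smallest, the test rejects too often. Among the first 29 patients, group 2 has both the largest PaCO2 SD and the fewest patients.

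The document also treats variances in two ways. Its pairwise table uses a procedure built for unequal variances, while the only overall test named for the final analysis is ordinarily understood to assume equal ones. At stake is whether the 0.05 level in item 5 holds for the overall comparison of an outcome that the protocol lists as primary for its second year.

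**Working it through.** **Inputs.** From Table II, second blood gas (labelled as in surgery there; the methods place it at the end of the operation): means 54.4, 86.4, 55.5; SDs 7.6, 21.7, 10.8; n = 11, 7, 11. Variances: 57.76, 470.89, 116.64. SD ratio 21.7/7.6 = 2.86; variance ratio 470.89/57.76 = 8.2. Group 2 also has the largest PaCO2 SD before surgery (9.5, against 2.5 and 6.5) and after it (9.0, against 4.0 and 5.7), so the pattern is not confined to one time point.

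**Step 1: reproduce the document's pairwise standard errors.** With separate variances, SE = sqrt(s1²/n1 + s2²/n2):

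- G1–G2: sqrt(57.76/11 + 470.89/7) = 8.516 (printed 8.5162)
- G1–G3: sqrt(57.76/11 + 116.64/11) = 3.982 (printed 3.9766)
- G2–G3: sqrt(470.89/7 + 116.64/11) = 8.825 (printed 8.8281)

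The pooled SD is sqrt[(10×57.76 + 6×470.89 + 10×116.64)/26] = 13.26. It would give 13.26 × sqrt(1/11 + 1/7) = 6.41 for G1–G2, which does not match. The pairwise tests already allow for unequal variances.

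**Step 2: direction of the error under no difference.** With N patients and 3 groups, the expected mean squares are:

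- between groups: Σ(N − n_i)σ_i² / (2N)
- within groups: Σ(n_i − 1)σ_i² / (N − 3)

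A valid F test needs these to be equal.

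- 11/7/11: between = (18×57.76 + 22×470.89 + 18×116.64)/58 = 232.7; within = 4569.3/26 = 175.7; ratio 1.32.
- 30/30/30: both equal (57.76 + 470.89 + 116.64)/3 = 215.1; ratio 1.00. Any remaining excess comes from the shape of the null distribution, so it should be small.
- 34/22/34 (the present split carried to 90: 90×11/29 ≈ 34, 90×7/29 ≈ 22): between = (56×57.76 + 68×470.89 + 56×116.64)/180 = 232.2; within = (33×57.76 + 21×470.89 + 33×116.64)/87 = 179.8; ratio 1.29.

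**Step 3: size of the error.** Simulated rejection rates at nominal 5%, with equal means, normal data and the SDs above:

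| Group sizes | Classical ANOVA | Welch's ANOVA |
|---|---|---|
| 11/7/11 (interim) | 11.8% | 5.2% |
| 30/30/30 (planned) | 6.5% | 5.0% |
| 30/27/30 | 7.5% | 4.9% |
| 30/24/30 | 8.7% | 5.0% |
| 30/20/30 | 10.8% | 5.0% |
| 34/22/34 | 11.0% | 5.0% |

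With equal SDs the same simulation returns 5.0% for the classical test at both 11/7/11 and 30/30/30, as it should.

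**Step 4: does the interim PaCO2 result depend on the choice?** From the Table II summaries, the classical test gives F = 14.96 on 2 and 26 df, p = 0.00005. For Welch's test, the weights n/s² are 0.1904, 0.0149 and 0.0943, and the weighted mean is 56.33. F = 7.108/1.0527 = 6.75 on 2 and 12.65 df, p = 0.010. Both are below 0.05.

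**Step 5: uncertainty in group 2's SD.** On 6 df the normal-theory 95% interval for 21.7 is about 14 to 48. With a true SD between 14 and 18, the classical level is between 5% and 6% at equal sizes and between about 7.5% and 9.6% at 34/22/34. At 48 it would be about 8.3% and 15.5%.

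**The case against.** The strongest reply is that the protocol plans equal groups. At 30 per group the level is about 6.5%, a small excess; the figure near 12% belongs to an interim look at 29 patients, and no passage plans 34/22/34. This stands. The pairing of the largest SD with the smallest group is a feature of the data so far, and it matters at the end only if group 2 stays behind.

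Second, item 3 does not assign ANOVA to PaCO2. This also stands. The link is by elimination, since the other listed tests are for categorical data.

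Third, the choice between Welch's and the classical ANOVA is often left to a statistical analysis plan, and the investigators clearly know how to handle unequal variances. This is only partly persuasive. The protocol is not silent: it names a test and prints data that contradict that test's usual assumption. Dunnett T3 appears only in the interim results, so nothing in the plan commits the final analysis to it.

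Two stronger readings are tempting and unsupported. A reader might infer that the pairwise contrasts, including relaxant-free versus intubated, will have distorted error bars. The document plans no pooled contrasts, and those it shows use separate variances. A reader might also infer that over-rejection runs through all the interim tables because other SDs are unequal. It does not: for operation time the smallest group has the smallest SD, for the first PaO2 the largest SD lies in a group of 11, and the simulated classical levels at 11/7/11 are close to nominal (4.6% and about 5.3%).

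**Conclusion.** The concern holds in a limited form and is minor to moderate. The named overall test is less valid for PaCO2 than a nearly free alternative: about 6.5% against 5% at the planned sizes, rising to about 11% if group 2 stays short in its present proportion. This rests on normal data and on true SDs equal to those observed, with group 2's SD estimated from 7 patients.

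The documents do not support saying that the final analysis will double its error rate, or that the interim PaCO2 difference is an artefact; that difference survives Welch's test. Nor is this a claim about which test produced the printed p-values. Some do not match a classical ANOVA on the printed summaries (for the second HCO3-, printed 0.06 against 0.02), and the document does not name the test behind them.

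**What to change.** In item 3, specify Welch's ANOVA for the continuous outcomes (blood gases, vital signs, operation time). Follow it with pairwise differences and 95% confidence intervals by Dunnett T3, as in Table VIII, or by Games-Howell. Name the blood gases explicitly so that the reader need not infer which test applies to them. Keeping group 2 on course for 30 patients would also limit the problem but would not replace the change of test.

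The cost is one sentence and no new data. The downside is a negligible loss of power if the variances prove equal. The change does not settle how item 3 should treat complications, severity and completion, which are not continuous.
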